## Questionnaire-

### Part II (only):

At enrollment and at their 14-day follow-up study visits, all Part 2 participants will complete a questionnaire that includes standardized scales to assess quality of life (QoL), depression, anxiety, and self-activation. Questionnaires will take approximately 45 minutes to complete. If a participant does not return for a follow-up study visit or is unable to complete an in-person questionnaire assessment, then a phone call will be made to the participant to see if they are willing to complete the questionnaire via a phone assessment. These participants will still need to return their devices to receive compensation. We will permit phone calls and assist with return by mail on a case-by-case basis.

We will compare changes from baseline to the 14-day follow-up in these measures between the Aim 2 intervention (n=90) and Aim 2 control (n=30) groups.

At the end of each participant's 44-day enrollment, they will complete a questionnaire either over the phone or in person, whichever is easier for the participant, to assess QoL, anxiety, and self-activation. This questionnaire will take approximately 20 minutes to complete. Participants who were not randomly chosen to use the Pulsewatch system for 30 days (Aim 3 control group) will receive compensation upon completion of the 44-day follow-up questionnaire. Participants who were randomly chosen to use the Pulsewatch system for 30 days (Aim 3 intervention group) will receive compensation upon completion of the 44-day follow-up questionnaire and return of their devices.

We will compare changes from the 14-day follow-up to the 44-day follow-up in these measures between the Aim 3 intervention (n=60) and Aim 3 control (n=60) groups.

We will create a short-form questionnaire assessment in the event that a participant is unable to complete the full questionnaire. The only difference between the full assessment and short form is that the short form will contain only outcome measurements for the questionnaire. Here is an overview of the variables our questionnaires will be collecting. We have uploaded all of our questionnaires to eIRB.

Measurement	Questionnaire Tool	Outcome or Stratifier	Baseline Assessment (All Part II)	14-Days Follow-up Assessment (Control)	14-Days Follow-up Assessment (Intervention)	44-Days Follow-up Assessme nt (All Part II)
Physical asses		•	•			
Vision	Questionnaire (4 items)	Stratifier	✓			
Hearing	Questionnaire (3 items)	Stratifier	$\checkmark$			
Psychosocial n						
Cognitive impairment	MoCA (30- items)	Stratifier	~			
Social support	Social Support Scale (5 items)	Stratifier	$\checkmark$			
	Lubben Social Network Scale (6 items)	Stratifier	~			
Depressive symptoms	PHQ-9	Stratifier	~			
Anxious symptoms	GAD-7	Outcome	~	~	~	~
Quality of life n	neasures	•				
Physical and mental health	Health survey SF-12 (12 items)	Outcome	✓	~	~	~
Patient activation	CHAI (10-items)	Outcome	✓	~	~	$\checkmark$
Disease management self-efficacy	Stanford Chronic Disease Management Self-Efficacy Scales: Manage Disease in General Scale (5 items)	Outcome	~	~	✓	
	Stanford Chronic Disease Management Self-Efficacy Scales: Manage Symptoms Scale (5 items)	Outcome	~	~	✓	
Medications						
Medication adherence	Adherence to Refills and Medication Scale (ARMS) (12- items)	Outcome	√	~	✓	
Health Related	Behavior					
Social history	Smoking and alcohol use	Stratifier	✓			
Other						
Interaction with provider	Perceived Efficacy in Patient – Physician interactions (PEPPI)	Stratifier	~			
Technology use	Device ownership/internet access	Stratifier	~			

## Pulsewatch ISP V 1.5 Docket#: H00016067

# PULSEWATCH INVESTIGATOR STUDY PLAN

Usability Assessment	System usability scale, Investigator generated questions	Outcome		$\checkmark$	
App usability assessment	Mobile Application Rating Scale (MARS) App Classification (11- items)	Outcome		√	
Demographics	Social economic status, employment, race and ethnicity questions	Stratifier	√		

# Aims 2-3: Questionnaire will include the following domains-

Anxiety: Anxiety will be assessed using the Generalized Anxiety Disorder-7 scale (GAD-7), a revised version of the anxiety module from the Patient Health Questionnaire, which consists of DSM-IV criteria for generalized anxiety disorder over the past 2 weeks. The GAD-7 score ranges from 0-27 with scores of 5, 10 and 15 representing validated cut-points for mild, moderate and severe levels of anxiety symptoms, with a score  $\geq$ 10 having high sensitivity (0.89) and specificity (0.82) for psychiatrist diagnosed anxiety disorder and correlates significantly with health-related QoL.

**Physical and mental health:** The SF-12 is a short form health survey to assess health related quality of life, this validated instrument domains include general health questions and mental health related questions. Scores range from 0 to 100, where higher scores indicate higher level of health.

**Patient Activation:** Patient activation refers to a patient's ability and willingness to manage their health Consumer health activation index (CHAI) is a 10-item scale. Scores range from 10 to 60 the higher the score the higher the activation the patient has for self-management of their condition. This is a validated questionnaire instrument.

**Cognitive function**: The Montreal Cognitive Assessment Battery (MoCA) is a 10-minute, 30-item screening tool designed to assist physicians in detecting mild cognitive impairment. MoCA correlates well (.89) with the widely used Mini Mental State Exam, but outperforms it in the detection of mild cognitive impairment (CI). The MoCA score can be used to examine a magnitude of change over time and offers validated, education-adjusted cut-points for mild CI and dementia..

**Social Support:** We will use a 5-item modified Social Support Scale and the 6-item Luben Social Network Scale. Together these measures assess breadth (e.g., help with activities) and depth (e.g., network size) of the participant's social support.

**Depressive Symptoms:** We will use the 9-item version of the Patient Health Questionnaire (PHQ-9), the depression module from the Patient Health Questionnaire, which can yield both a provisional diagnosis of depression and a severity score that are associated with functional status, disability days and healthcare utilization. The PHQ-9 consists of the 9 criteria upon which DSM-IV depressive disorders are based. Using a cut-point of  $\geq$ 10 (range = 0-27), the PHQ-9 has high sensitivity (.88) and specificity (.88) for detecting major depression among patients with CVD.Study staff will follow UMass Extreme Emotional Distress protocol approved by the IRB in the event that a patient indicates suicidal thoughts.

**Vision**: We will test vision using a Snellen eye chart. Participants will also be asked the question, 'How much does your vision interfere with your activities?' based on a 4-point Likert scale from 'not at all' to 'a lot'.

**Hearing:** We will use the Whisper test where participants are asked to repeat back numbers whispered into their ear. Impairment is defined as hearing ≤6 of 12 numbers. We will complement objective hearing assessments with subjective self-reported responses to the question: 'How much does your hearing interfere with your activities?'

**Disease Management Self-Efficacy:** Self-efficacy for disease management is associated with engagement in health behaviors and with improved medication adherenceThe General Disease Management scale is a 5-item scale assessing confidence in disease self-management (scores 0-50, higher scores = greater confidence). The Symptom Management scale is a 5-item scale assessing confidence in managing chronic disease symptoms (items tailored to sample).

Medication Adherence: Medication adherence will be measured using the 12-item Adherence to Refills and Medications Scale (ARMS), a well-validated measure of patient-reported adherence. ARMS scores range from 1-4 (higher scores=poorer adherence).

**Social history:** Social and behavioral factors such as smoking and alcohol use are related to strokes and cardiovascular conditions. Given that the goal of this study is to prevent recurring strokes in this patient population, we believe it is necessary to obtain this information from participants.

App usability: Mobile Application Rating Scale (MARS) App Classification (11-items) these questions will help us capture the participants experience with the application.

## Deployment of devices/app-

**Part I**: Participants will use the Pulsewatch System prototype version of the app (AFExam), a smartphone, and a smartwatch during focus groups or a Hack-a-thon to provide feedback for further development of the app, and to enhance the deployment of the system in Part II of the study.

**Part II:** We will provide up to 120 randomly selected participants with an Android smartphone if they do not own a compatible phone. The smartphone will be active – meaning we will pay for a standard cellular data/voice/text plan for the duration of the study period. The smartphone will be preloaded with a Samsung application to enable communication with the smartwatch, the study software application, the AliveCor Kardia application (used in Aim 3), the participant, and the study team. Participants who are selected for the intervention arm of Aim 3 will be given the AliveCor Kardia application, commercially available, single-lead ECG recording device that communicates with the smartphone. Participants will also be provided with a smartwatch and a handout outlining how to use the devices (see in eIRB, Device Handout). We will ask participants to wear the smartwatch day and night for 14 days, removing it only to charge each morning or during a shower. The Pulsewatch app interface will allow participants to enter into the app symptoms they may feeling.

We have selected the Galaxy Android smartphone because it can interface seamlessly with the Samsung smartwatch. If participants have compatible phones they want to use for the study, we will download the Pulsewatch and AliveCor apps onto their phones, and we will pair their phones with the Samsung study watch. We will also provide compensation to participants when they return the smartphone and watch to study staff after completing the study. Participants will be encouraged to call study staff with any problems encountered when using Pulsewatch during the 14-day monitoring period.

Participants will also have a cardiac patch placed on their chest at enrollment. This monitor will serve as a gold-standard comparator in our study and is a diagnostic-grade, FDA-approved, and fully regulated medical device manufactured by Cardiac Insight. The gold-standard cardiac patch will be placed onto participants by trained study staff at enrollment. Participants will be instructed to call the study team if they have any problems with the monitor.

Research staff (RA or study coordinator) will provide enrolled participants with detailed instructions about the operations and proper usage of the Pulsewatch smartwatch, smartphone

apps (including the Pulsewatch app and AliveCor app), ECG, and 14-day monitor. A checklist and a YouTube video may be made available to participants to remind them of how to charge. wear, and perform ECG self-checks using the smartwatch and phone app. Participants (including all control and intervention participants) will return smartphones and watches and/or 14-day monitors after their study visit at 14 days. For Aim 2 intervention participants, pulse and ECG data from the smartwatch and annotations/adherence data from smartphones will be uploaded by study staff after the 14-day visit to the secure cloud server. Aim 2 control participants will be provided instructions on the gold-standard Cardiac Insight patches. Study staff will be available via telephone to answer any questions participants have with using the smartwatch and smartphone, charging the battery, and uploading data throughout the 14-day trial period as needed. The 60 randomly selected participants, who were consented at baseline to participate in this aim will receive additional training at their 14-day study visit, taught on how to use the AliveCor Kardia mobile device and will use the Pulsewatch smartwatch and smartphone for an additional 30 days. Participants in Aim 3's intervention group will be asked to upload pulse and ECG data from AliveCor if they would like to do a self-check after receiving the watch notification. The secure server architecture used by Samsung minimizes the potential for loss of health information and is similar to one used in our prior work.

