All participants will be given a Device Handout regarding instruction for the appropriate devices they are given. In addition, the study team will review with each participant all instructions regarding how the Cardiac Insight patch functions and the participant's responsibility. The participant will also go home with information regarding the patches (see in eIRB, Cardea Solo Quick start guide- this will be added the Device handout). The study team, specifically the PI, may need to contact participants directly about their results. This will be disclosed in the informed consent form that participants sign.

The Aim 2 intervention participants (up to n=90) will be asked to use the same gold-standard Cardiac Insight patch monitor device for 14 days as the control group described above. Aim 2 intervention participants will also be given a Samsung smartwatch and a Galaxy smartphone. The Samsung smartwatch and Galaxy smartphone are standard devices that are sold commercially and will be labeled, nonetheless, as research devices. If the participant has a smartphone that is compatible to our Pulsewatch app, then we will download the app onto the participant's smartphone.

The Aim 2 intervention group (up to n=90) will be asked to self-monitor using the Pulsewatch system for at least 9 hours daily for 14 days. The intervention system is designed to be minimally intrusive. Participants will be asked to return all study devices (2 Cardiac Insight patches, Samsung smartwatch, and Galaxy smartphone) at the end of their 14 days of use at the follow-up study visit. Participants will be asked to complete a questionnaire at this follow-up study visit and will be compensated.

At enrollment in Part II, all study participants will be informed of the possibility that they may be randomly selected at the completion of their 14-day monitoring period to use the Pulsewatch system for up to 30 days. We chose to assign a larger proportion of participants to the Aim 2 intervention group because the primary analyses for Aims 2 and 3 are focused on Pulsewatch users.

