## **AF Detection Analysis:**

Analysis for the study focus on the performance of daily wear of the Pulsewatch system for 9 hours compared to standard Cardiac Insight patch monitoring over the course of 14 days. We will examine the system's accuracy for pAF identification as well as estimation of AF burden. A participant will be classified as having pAF or not at the end of the 14-day monitoring period based on the gold standard monitor. Data from the Pulsewatch is divided into 30-second segments for analysis and a positive reading will be defined as AF being detected in at least 7 out of 10 continuous data windows (5 minutes). The total number of positive readings collected over 14 days from Pulsewatch will be used as the independent variable in a logistic regression to predict the binary outcome of pAF (yes vs. no). The area under the receiver operating characteristic (ROC) curve (AUC) will be calculated based on the results from the logistic regression to evaluate Pulsewatch performance for pAF screening. From the ROC curve, we can identify the cutoff point of total number of positive readings that produces the highest sensitivity and specificity combination.

Preliminary data suggest that Pulsewatch will have sensitivity, specificity and AUC of at least .9 to detect pAF. Assuming .

Similar analysis will be conducted using the % of positive readings among all readings collected from each participant as the independent variable. The 95% confidence intervals (CI) of the AUC will be calculated using formula given by Hanley and McNeil. We will then conduct exploratory analyses to examine whether characteristics affect watch performance over 14 days. For example, we will compare the area under 2 independent ROC curves of female vs. male participants (or vision impaired vs. not) using a chi-square test. At the end of 14-days we will review the data of 45 participants in Aim 2 intervention and see what % of participants have AF. If we see less than 5% of all participants using the devices have AF, we will have an adaptive protocol for analysis. We would ask participants to extend their use of the devices for an additional 14-days and continue to monitor the participants for potential AF cases. Their follow up assessment for participants in Aim 2 of Part II would be at the end of the 28 days if we take this approach.

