Determine effects of patient characteristics on Pulsewatch performance	2	90 Pulsewatch users	Area under the curve	Patient characteristics (e.g., sex, hearing or visual impairment)	Chi-square test to compare AUC of 2 independent ROC curves
Examine Pulsewatch usability	3	30 Pulsewatch users	Indicator of watch daily use (yes vs. no) over 1 month	Sex, cognitive function, social support, depression, Barthel)	Mixed effects logistic regression model
Evaluate the impact of Pulsewatch use on key patient-reported outcomes	3	30 Pulsewatch users and 30 controls	Stroke-related quality of life, anxiety & self-activation (Δ from baseline -1 mo)	Potential confounders (e.g. sex, medication adherence and disease-management self-efficacy)	t-test and linear regression model

Aim 2 Analysis: The analysis will focus on examining the performance of Pulsewatch worn for 9 hours daily for 14 days compared to 14-day cardiac monitoring, CardioKey by Biotel. A participant will be classified as having or not having pAF at the end of 14 days based on the gold standard. The total number of positive readings collected over 14 days from Pulsewatch (min 1 pulse every 5 minutes for 504 samples) will be used as the independent variable in a logistic regression to predict the binary outcome of pAF (yes vs. no). The area under the receiver operating characteristic (ROC) curve (AUC) will be calculated based on the results from the logistic regression to evaluate Pulsewatch performance for pAF screening. From the ROC curve, we can identify the cutoff point of total number of positive readings that produces the highest sensitivity and specificity combination. Similar analysis will be conducted using the % of positive readings among all readings collected from each participant as the independent variable. The 95% confidence intervals (CI) of the AUC will be calculated using formula given by Hanley and McNeil. We will then conduct exploratory analyses to examine whether characteristics affect watch performance over 14 days. For example, we will compare the area under 2 independent ROC curves of female vs. male participants (or vision impaired vs. not) using a chi-square test.

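### The Aim 2 analysis is said to evaluate 9 hours of daily wear, but participants are told to wear the watch day and night, and a cutoff on a raw count of positive readings does not carry over between the two.

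*Protocol*

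**What the plan says.** Four places describe wear time in Aim 2.

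- Protocol section 11, Part II, asks the intervention group to "self-monitor using the Pulsewatch system for at least 9 hours daily for 14 days".
- Protocol section 11, Deployment of devices/app: "We will ask participants to wear the smartwatch day and night for 14 days". The only exceptions are the morning charge and showering.
- Protocol section 13, AF Detection Analysis, gives the target of the analysis as "the performance of daily wear of the Pulsewatch system for 9 hours compared to standard Cardiac Insight patch monitoring".
- The SAP, Aim 2 Analysis, likewise speaks of "examining the performance of Pulsewatch worn for 9 hours daily for 14 days compared to 14-day cardiac monitoring".

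On the predictor, section 13 states: "The total number of positive readings collected over 14 days from Pulsewatch will be used as the independent variable". The SAP agrees. The next step in both is a cutoff chosen from the ROC curve, and it is defined on that total. A parallel analysis with the percentage of positive readings follows. SAP Table 2 lists number and percentage together. Neither is called primary.

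Section 13 defines a positive reading on a block of ten 30-second windows, that is, five minutes. The SAP gives a minimum of one pulse per 5 minutes and 504 samples over the 14 days.

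**The concern.** The regimen named in the analysis is not the one that the deployment text asks participants to follow. No rule picks out a 9-hour window from a longer recording, sets a wear range for inclusion, or brings hours worn into the model. If participants follow the deployment text, the reported AUC and cutoff will be attributed to 9-hour wear although they come from near-continuous wear.

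The count makes this worse. At a fixed rate of false-positive blocks, positives accumulate with hours recorded, so a long wearer without AF can outscore a short wearer with AF. At stake are the label on the main performance result and the meaning of the cutoff that a later user of the watch would apply.

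**Working it through.** **The plan's own precision figure.** The inputs are in SAP Aim 2 Power: 90 users, 20% with pAF (18 with, 72 without), AUC .90 to .95. The Hanley-McNeil variance is [A(1−A) + (n1−1)(Q1−A²) + (n0−1)(Q2−A²)]/(n1·n0), with Q1 = A/(2−A) and Q2 = 2A²/(1+A).

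- A = .90: SE = .0501, width = 2 × 1.96 × .0501 = .196.
- A = .95: SE = .0365, width = 2 × 1.96 × .0365 = .143.

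The SAP states .14 to .20, so its figure is reproduced. The half-widths are about .07 and .10.

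**Reading slots.** Slots = hours per day × 12 per hour × 14 days.

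| Hours per day | Slots over 14 days |
|---|---|
| 9 | 1,512 |
| 23 (assumed for day-and-night wear) | 3,864 |
| 24 (upper bound) | 4,032 |

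The ratios to 9 hours are 2.56 and 2.67. The SAP's 504 equals 3 × 12 × 14, which is 3 hours a day, or one reading per 15 minutes over 9 hours. The protocol's usable-data shares of 50% (active) and 90% (rest) do not explain it: 1,512 × .5 = 756 and 1,512 × .9 = 1,361.

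**Effect on the AUC.** The documents give no false-positive rate or AF burden, so this part is illustrative. Four settings were simulated with 200,000 participants each, 20% pAF, mean false-positive block rates of .5% to 2%, and mean AF burdens of 2% to 5%.

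| Wear pattern | Count AUC minus percentage AUC |
|---|---|
| All at 9 h, or all at 23 h | 0 |
| 9–23 h, unrelated to pAF | −.004 to −.015 |
| Half at 9 h, half at 23 h | −.01 to −.04 |
| Shorter in pAF (9–16 h) | −.03 to −.06 |
| Longer in pAF (16–23 h) | +.02 to +.03 |

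The percentage AUCs were .81 to .87, below the .90 to .95 that the SAP assumes.

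**Effect on the cutoff.** Assume a 2% false-positive block rate.

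- No AF, 9 h: .02 × 1,512 = 30 positives.
- No AF, 24 h: .02 × 4,032 = 81 positives.
- AF adding a further 2%, 9 h: .04 × 1,512 = 60 positives.

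A count cutoff of 60 separates the two 9-hour wearers correctly but flags the 24-hour wearer without AF. The same cutoff corresponds to 60/1,512 = 4.0% of slots at 9 hours and 60/4,032 = 1.5% at 24 hours. On the percentage scale the three people stand at 2%, 2% and 4%, in the right order.

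Simulation agrees. With a mean false-positive rate of 2%, log-normal spread of .3 to 1.0 and mean burden of 2% or 5%, the best count cutoff at 9 hours had specificity .63 to .95. Applied unchanged at 23 hours, it had .04 to .47. A separate rerun gave .64 to .99 falling to .03 to .83.

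**The case against.** The strongest reply has three parts.

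First, a reader might infer that participants receive two contradictory instructions. The documents do not support that. The instruction in section 11, Part II, is a minimum, and day-and-night wear meets it. The mismatch is between the deployment text and the analysis text of section 13 and the SAP.

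Second, a reader might infer that the plan overlooks exposure time. It does not: the percentage analysis is already specified in both documents, and the count leads only by order of listing. What stands is that no primary predictor is named and the cutoff is defined on the total alone.

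Third, a reader might infer that the AUC is biased downward. AUC depends on ranks, so uniform wear leaves it unchanged. With wear of 18 to 23 hours, roughly what the deployment text would produce, the gap between the two AUCs was .000 to .005 in a rerun with false-positive rates of .1% to 2%. At a .1% rate it was at most .014 even with wear of 9 to 24 hours. The rule of 7 windows in 10 may well hold the false-positive rate down. The direction can also reverse if people with pAF wear the watch longer.

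In answer, a 9-hour minimum beside a day-and-night request allows wide variation, and the SAP itself anticipates uneven adherence, with strata from below 50% to above 75%, although for Aim 3. None of the three parts rescues a count cutoff used across wear patterns.

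**Conclusion.** The concern holds in a limited form. The regimen named in section 13 and the SAP differs from the one in the deployment text, no rule for hours worn connects them, and the 504 figure fits neither. These points rest on the text and simple arithmetic.

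The effect on the AUC is conditional: none under uniform wear, and about .00 to .06 when wear varies, in either direction if wear is related to pAF. That is within the planned half-width of .07 to .10 and depends on assumed false-positive and burden rates, so a material bias in the AUC is not shown.

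The cutoff is the exposed result. The slot count differs up to 2.67-fold between the two wear patterns, so one count threshold stands for different positive rates. The size of the loss in specificity again depends on the assumed rates. The matter should be corrected before analysis; it does not undermine the design.

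**What to change.** Reconcile the deployment text, section 13 and SAP Aim 2 Analysis, including the 504 figure, so that the regimen named in the conclusion is the one participants are asked to follow. Which regimen that should be is for the investigators.

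In the SAP, name the percentage of positive readings as the lead predictor and the source of the cutoff, keep the count as secondary, and report recorded hours per day beside the AUC.

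The cost is wording only, since both analyses are already planned. There are two limits. The percentage is less stable in participants with few readings. It also does not settle which regimen is being evaluated, because AF outside worn hours is seen by the patch and not by the watch.
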